Concept and Rationale:

Disease Background: For men who previously received definitive treatment for prostate cancer and subsequently develop detectable prostate specific antigen (PSA), the clinical state is known as biochemically recurrent prostate cancer. The natural history for these patients is variable, and the risk for development of metastasis depends on the PSA Doubling Time (PSADT). For patients with PSADT < 6 months, the median metastasis-free survival is ~2 years in the absence of androgen deprivation therapy (ADT). The current standard of care treatment for patients with high risk biochemically recurrent prostate cancer is either surveillance or ADT. ADT has not been shown to provide a survival benefit in this setting, and the decision to initiate ADT will depend on patient preference and perceived risks of the disease. A non-hormonal therapy such as olaparib would provide an alternative to ADT as a potential treatment option for these patients.

Investigational Agent: Olaparib is a poly-ADP ribose polymerase (PARP) inhibitor that is FDA-approved for the treatment of advanced, refractory ovarian cancer. PARP functions in the DNA repair pathway, specifically by serving in base excision repair of DNA single strand breaks. Inhibition of PARP results in inability for cells to repair single strand breaks. Cells normally would employ the error-free homologous recombination pathway to repair such defects. However, in tumors that harbor defects in these DNA repair genes (such as BRCA1/2 or ATM), the strand breaks lead to chromosomal instability and eventually cell death. Olaparib also traps the PARP protein on DNA, leading to further cytotoxicity. A dose of 300mg (tablets) PO BID, which is bioequivalent to the FDA-approved dose of 400mg (capsules) PO BID, will be employed in this study.

Rationale for olaparib in high risk biochemically recurrent prostate cancer: Olaparib has demonstrated preliminary efficacy in metastatic castration-resistant prostate cancer. In a trial of 49 evaluable patients treated with olaparib, 11 / 49 experienced a PSA₅₀ response, and every patient with a radiographic response also had a PSA₅₀ response. Ten of 11 responders had mutations in DNA repair genes. While PARP inhibition is showing promise in these initial studies, reserving its use for end-stage patients may not be the optimal timing for olaparib therapy in some patients. In addition, PARP enzymes function in roles beyond DNA repair, and specifically for prostate cancer are involved transcriptional regulation of the androgen receptor. PARP inhibition has not been tested in earlier disease states for prostate cancer.

Several studies have recently been published describing the prevalence of DNA repair defects in prostate cancer. Based upon these large genomic analyses for cohorts of patients with prostate

cancer, we can estimate a range of likely prevalence for DNA repair defective tumors for patients with biochemically recurrent prostate cancer. For mutations detectable in tumor tissue, the prevalence for biochemically recurrent prostate cancer is likely between the 19-23%. The anticipated range for germline mutations is 5-12%. Therefore, the defects that likely predict sensitivity to olaparib are likely present in some of these patients. Yet, despite some encouraging preliminary data on a potential mutation signature that is predictive of response to olaparib, the optimal biomarker profile for response is probably not known at this time.

Rationale for correlative studies

Tumors will be sequenced for somatic genetic mutations in DNA repair genes (Foundation Medicine). The genes analyzed will include those commonly mutated (BRCA2, ATM, BRCA1, CHEK2, CDK12, RAD51, PALB2, FANCL). By cataloging the mutations present in the primary tumors for subjects in the study, correlative analysis associating response with specific mutations can be performed.

An alternative biomarker for tumor sensitivity to olaparib is through gene expression changes that may not be identified through genetic mutation analysis alone. Subjects will have tissue tested for RNA expression arrays for associating response to olaparib. For this assay, samples will be tested using the Decipher GRID microarray platform (GenomeDx). The gene expression profile will be inclusive of a metastasis signature and olaparib-sensitivity signature. A post-hoc analysis will be performed to evaluate these signatures, and further determine a gene expression profile that predicts response to olaparib.

An exploratory biomarker, beyond the DNA mutations and RNA expression changes, is a functional examination of PARP activity in the tumor. A protein-level assessment of PARP-1 and γ H2AX through immunohistochemistry will be performed on prostatectomy tumor tissue. PARP-1 is the primary target of olaparib, and γ H2AX is a protein present at sites of double strand DNA breaks. The expression of these markers will be qualitatively scored and levels of expression correlated with response to olaparib.

Primary Objective: To estimate the PSA response rate to olaparib in patients with high-risk biochemically recurrent prostate cancer while on treatment with olaparib, defined as a decline in PSA to 50% of baseline level, confirmed with a second measurement at least 4 weeks apart.

Secondary Objectives:

- To determine the safety/tolerability of olaparib in the biochemically-recurrent prostate cancer patient population.
- To estimate the median PSA progression-free survival.
- To estimate the median time to PSA doubling from baseline.
- To estimate the rate of durable undetectable PSA in patients responding to olaparib.

Exploratory Objectives:

- To estimate PSA₅₀ response in “biomarker positive” patients, based upon tissue-based FoundationOne mutations in the pre-specified gene list (ATM, BARD1, BRCA1, BRCA2, BRIP1, CDK12, CHEK1, CHEK2, FANCL, PALB2, PPP2R2A, RAD51B, RAD51C, RAD51D, or other DNA repair genes), if an enriched cohort is not accrued.
- To estimate PSA₅₀ response in “biomarker negative” patients, based upon tissue-based mutations in the pre-specified gene list, if an enriched cohort is not accrued.

- To estimate PSA₅₀ response rate for patients with and without a mutation on the pre-specified list, based upon plasma cell-free DNA analysis using the pre-specified gene list (ATM, BARD1, BRCA1, BRCA2, BRIP1, CDK12, CHEK1, CHEK2, FANCL, PALB2, PPP2R2A, RAD51B, RAD51C, RAD51D, or other DNA repair genes).
- To develop a genetic mutation signature associated with response to olaparib. For this objective, the biomarker signature will not be defined *a priori* but instead this will involve an exploratory analysis.
- To develop an RNA expression signature associated with response to olaparib.
- To investigate any association between PARP-1 and γ H2AX protein levels in tumor with response to olaparib.
- To estimate median metastasis-free survival.
- To estimate median time to next anti-cancer therapy.

Primary Endpoint: PSA₅₀ response, defined as a decline in PSA to 50% of baseline level, confirmed with a second measurement at least 4 weeks apart.

Secondary Endpoints:

- Safety/Tolerability, defined as incidence of CTC v4.0 grade ≥ 3 toxicities experienced by patients on the trial.
- PSA progression-free survival, defined as a time from initiation on olaparib therapy until PSA increase of 25%, confirmed with another measurement at least 4 weeks later.
- Time to PSA doubling from baseline, defined as time from initiation of olaparib therapy until the PSA has increased to 200% of baseline value, confirmed with another measurement at least 4 weeks later.
- Undetectable PSA, defined as PSA < 0.1 , lasting at least 12 weeks.

Exploratory Endpoints:

- (*If an enriched population is not accrued*) PSA₅₀ response, defined as a decline in PSA to 50% of baseline level, confirmed with a second measurement at least 4 weeks apart, in “biomarker positive” patients based upon tissue-based testing for the pre-specified gene list (ATM, BARD1, BRCA1, BRCA2, BRIP1, CDK12, CHEK1, CHEK2, FANCL, PALB2, PPP2R2A, RAD51B, RAD51C, RAD51D, or other DNA repair genes).
- (*If an enriched population is not accrued*) PSA₅₀ response, defined as a decline in PSA to 50% of baseline level, confirmed with a second measurement at least 4 weeks apart, in “biomarker negative” patients, based upon tissue-based testing for the pre-specified gene list.
- PSA50 response, defined as decline in PSA to 50% of baseline level, confirmed with a second measurement at least 4 weeks apart, in “biomarker positive” and “biomarker negative” patients, based upon plasma cell-free DNA analysis and the pre-specified gene list.
- To develop a DNA mutation signature for response based upon prostatectomy sample testing.
- To associate RNA expression array signature with response.
- To associate response to olaparib with baseline PARP-1 and γ H2AX protein levels in prostatectomy specimens.

- Metastasis-free survival, defined as time from biochemical recurrence to radiographic development of metastatic disease.
- Time to next anti-cancer therapy, defined as time from biochemical recurrence to date of administration of prostate cancer therapy (such as ADT, oral antiandrogen, or other clinical trial agent).

Study Design: The proposed study is an open-label single-arm phase II trial. Eligible patients are those with non-metastatic biochemically-recurrent prostate cancer and a PSADT of ≤ 6 months and a minimum PSA of 1.0. After enrollment, patients will be treated with olaparib at the established dose of 300mg tablets by mouth twice daily. Patients will be followed monthly with clinic visits, safety labs (including CBC w/diff, Comp), PSA, and toxicity assessments. Treatment [with a minimum drug exposure of 12 weeks] will be continued until PSA doubling from study entry (confirmed with another measurement at least 4 weeks later), development of radiographic metastatic disease, or toxicity requiring drug cessation. CT scans and NM bone scans will be performed every 6 months for patients remaining on olaparib treatment.

After enrollment, patients will have tissue from their primary prostatectomy specimens sequenced for genomic DNA changes potentially predictive of olaparib response using the Foundation Medicine sequencing platform. In addition, tissue will be analyzed with RNA expression arrays using the Decipher GRID microarray platform (GenomeDx). The gene expression profile will be inclusive of a metastasis signature and olaparib-sensitivity signature. Tissue will also be analyzed for protein levels of PARP-1 and γ H2AX at baseline. Plasma will be collected for cell-free DNA analysis.

This study will enroll up to 50 subjects. The study design will employ a stepwise adaptive statistical plan, derived in part from Biankin *et al*, *Nature* 2015 Oct 15;526(7573):361-70. The design is adapted from a multi-stage design, with interim stopping rules to determine futility or need for enrichment of the study population.

The study will initiate with a two-stage design in an unselected population. The assumptions for the trial of the unselected population are: null hypothesis of 0.1 PSA response rate and alternative hypothesis of 0.3 for the unselected population. The first stage is 20 subjects. If ≤ 2 subjects respond in the first stage, then unselected population study is halted for futility and an assessment of DNA mutations present in the initial cohort will be undertaken. If less than 3 subjects with a known/suspected deleterious mutation in the following genes (ATM, BARD1, BRCA1, BRCA2, BRIP1, CDK12, CHEK1, CHEK2, FANCL, PALB2, PPP2R2A, RAD51B, RAD51C, RAD51D, or other DNA repair genes) have been accrued in the first stage, then the trial will proceed with enrichment. If 3 or more subjects with known/suspected deleterious mutation in the genes of interest have been accrued, then the trial will proceed with enrichment, as long as the response rate in that subset of subjects is $\geq 20\%$. In the case that 3 or more subjects have been accrued, yet the response rate in that subset is $< 20\%$, then the trial is halted for futility.

[figure not shown]
However, if ≥ 3 subjects among the first 20 respond, then additional 10 unselected subjects are accrued. If ≥ 6 subjects respond out of 30 in the unselected population after the second stage, then the null hypothesis is rejected in the unselected population and broad efficacy will be concluded. The trial proceeds to complete accrual of 50 subjects in order to better estimate PSA response rate and strengthen data for correlative studies. If < 6 respond, then the null hypothesis is not rejected. Again, if less than 3 subjects with a known/suspected deleterious

mutation in the following genes (ATM, BARD1, BRCA1, BRCA2, BRIP1, CDK12, CHEK1, CHEK2, FANCL, PALB2, PPP2R2A, RAD51B, RAD51C, RAD51D, or other DNA repair genes) have been accrued in the first and second stage combined, then the trial will proceed with enrichment. If 3 or more subjects with those mutations have been accrued, then enrichment will again proceed as long as the response rate in that subject of subjects is $\geq 20\%$.

An enriched population will be required to have a known/suspected deleterious mutation in of the genes listed above. The data for the enriched population will be analyzed separately from the data in the first (and second, if applicable) stage(s). The assumptions for the enriched population: null hypothesis of 0.3 PSA response rate, and alternative hypothesis of 0.6 for the biomarker selected population. The sample size for the selected population is 20 subjects. If ≥ 10 respond, the null is rejected for the biomarker selected population and efficacy will be concluded for the biomarker subgroup.

This design will have power for detecting an effect in the unselected population of 0.90-0.91 and a power for detecting an effect in the selected population (if there is no effect in the unselected) of 0.79-0.80, with an overall type I error 0.1-0.11, assuming the biomarker prevalence 10-15%, based upon 10,000 simulations of possible outcomes.

Schema:

Number of Patients: 50.

Our institution has a record of accruing 1-2 patients per month to trials in patients with biochemically recurrent prostate cancer with similar inclusion criteria. With opening at multiple sites, trial would be expected to fully accrue in 24 months or less. The primary endpoint is expected to be reportable within 30 months, or sooner, after trial activation.

Main Eligibility Criteria:

Inclusion:

1. Histologic diagnosis of adenocarcinoma of the prostate.
2. Prior local therapy with prostatectomy required, with available tissue from prostatectomy specimen to send for genomic and transcriptomic testing.
3. Prior salvage or adjuvant radiation therapy is allowed but not mandated. Radiation therapy must have been completed for at least 6 months.
4. Absolute PSA ≥ 1 ng/ml. Prior undetectable PSA post-prostatectomy is not required.
5. PSADT ≤ 6 months, based upon ≥ 3 consecutive measurements collected in the past 12 months, at least 4 weeks apart, calculated using MSKCC calculator
6. No radiographic evidence of metastatic disease by CT scan and bone scan, performed within the prior 4 weeks.
7. Serum testosterone ≥ 150 ng/dl.
8. Participants must have normal organ and bone marrow function measured within 28 days prior to administration of study treatment as defined below:
 - Hemoglobin ≥ 10.0 g/dL with no blood transfusion in the past 28 days
 - Absolute neutrophil count (ANC) $\geq 1.5 \times 10^9$ /L
 - Platelet count $\geq 75 \times 10^9$ /L
 - Total bilirubin $\leq 1.5 \times$ institutional upper limit of normal (ULN)
 - Aspartate aminotransferase (AST) (Serum Glutamic Oxaloacetic Transaminase (SGOT)) / Alanine aminotransferase (ALT) (Serum Glutamic Pyruvate Transaminase (SGPT)) $< 2.5 \times$ institutional upper limit of normal

Note: Patients with elevations in bilirubin, AST, or ALT should be thoroughly evaluated for the etiology of this abnormality prior to entry and patients with evidence of viral infection should be excluded.

- Patients must have creatinine clearance estimated using the Cockcroft-Gault equation of ≥ 51 mL/min:
Estimated creatinine clearance = $\frac{(140 - \text{age [years]}) \times \text{weight (kg)}}{\text{serum creatinine (mg/dL)} \times 72}$

9. Eastern Cooperative Oncology Group (ECOG) performance status 0-1 (see Appendix A).
10. Male participants and their partners, who are sexually active and of childbearing potential, must agree to the use of two highly effective forms of contraception in combination [see appendix E for acceptable methods], throughout the period of taking study treatment and for 3 months after last dose of study drug to prevent pregnancy in a partner.
11. *For enrichment stage of trial only (if necessary):* Confirmation of a suspected/known deleterious mutation in a gene of interest (ATM, BARD1, BRCA1, BRCA2, BRIP1, CDK12, CHEK1, CHEK2, FANCL, PALB2, PPP2R2A, RAD51B, RAD51C, RAD51D, or other DNA repair genes) via CLIA certified testing.

Exclusion:

1. Prior ADT in the past 6 months. Prior ADT in context of neoadjuvant/adjuvant primary; prior ADT for biochemical recurrence is allowed, as long as no ADT has been administered in past 6 months and testosterone has recovered (>150 ng/dl). The total duration of prior ADT should not exceed 24 months.

2. Prior oral anti-androgen (e.g. bicalutamide, nilutamide, enzalutamide, apalutamide), or androgen synthesis inhibitor (e.g. abiraterone, orteronel) in the past 6 months. 5-alpha reductase inhibitor therapy (e.g. finasteride, dutasteride) is allowed, as long as subject has been stable on medication for past 6 months.
3. Prior treatment with intravenous chemotherapy for prostate cancer.
4. Involvement in the planning and/or conduct of the study (applies to both AstraZeneca staff and/or staff at the study site)
5. Participation in another clinical study with an investigational product during the last 1 month.
6. Any previous treatment with PARP inhibitor, including olaparib.
7. Resting ECG with QTc > 470 msec on 2 or more time points within a 24 hour period or family history of long QT syndrome
8. Concomitant use of known strong CYP3A inhibitors (eg. itraconazole, telithromycin, clarithromycin, protease inhibitors boosted with ritonavir or cobicistat, indinavir, saquinavir, nelfinavir, boceprevir, telaprevir) or moderate CYP3A inhibitors (eg. ciprofloxacin, erythromycin, diltiazem, fluconazole, verapamil). The required washout period prior to starting olaparib is 2 weeks.
9. Concomitant use of known strong CYP3A inducers (eg. phenobarbital, enzalutamide, phenytoin, rifampicin, rifabutin, rifapentine, carbamazepine, nevirapine and St John's Wort) or moderate CYP3A inducers (eg. bosentan, efavirenz, modafinil). The required washout period prior to starting olaparib is 5 weeks for phenobarbital and 3 weeks for other agents.
10. Myelodysplastic syndrome/acute myeloid leukaemia or with features suggestive of MDS/AML.
11. Major surgery within 2 weeks of starting study treatment and patients must have recovered from any effects of any major surgery.
12. Poor medical risk due to a serious, uncontrolled medical disorder, non-malignant systemic disease or active, uncontrolled infection. Examples include, but are not limited to, uncontrolled ventricular arrhythmia, recent (within 3 months) myocardial infarction, uncontrolled major seizure disorder, extensive interstitial bilateral lung disease on High Resolution Computed Tomography (HRCT) scan or any psychiatric disorder that prohibits obtaining informed consent.
13. Unable to swallow orally administered medication and patients with gastrointestinal disorders likely to interfere with absorption of the study medication.
14. Immunocompromised patients, e.g., patients who are known to be serologically positive for human immunodeficiency virus (HIV).
15. Known hypersensitivity to olaparib or any of the excipients of the product.
16. Known active hepatitis (i.e. Hepatitis B or C) due to risk of transmitting the infection through blood or other body fluids
17. Whole blood transfusions in the last 120 days prior to entry to the study (packed red blood cells and platelet transfusions are acceptable, for timing refer to inclusion criteria no.10)

Intervention and Mode of Delivery: Olaparib 300mg tablets by mouth twice daily.

Duration of Intervention and Evaluation: Patients will be treated until toxicity requiring cessation, doubling of PSA from baseline, confirmed by a second measurement at least 4 weeks apart, or clinical/radiographic progression, defined as development of symptoms related to prostate cancer or metastatic disease on CT or NM Bone Scan. Patients will be monitored monthly while on therapy. After completion of study treatments, they will be monitored for at least 1 month after any grade 2 or higher toxicities return to grade 1 or resolve.

Statistical Methods:

(a) Definition of primary endpoint: The primary endpoint of this study is PSA₅₀ response, defined as a decrease in the PSA to 50% less than the baseline PSA upon enrollment in the trial. The decrease must be confirmed by a second measurement at least 4 weeks apart. For purposes of meeting the primary endpoint, patients will be considered to have done so if they have a PSA₅₀ response only while on therapy with olaparib. PSA values will be measured monthly during the trial. All patients who are administered at least one dose of olaparib will be considered evaluable for the primary endpoint. If patients do not have follow-up PSAs after initiation olaparib therapy due to stopping therapy for toxicity or withdrawing consent, then they will be considered non-responders. If the biomarker-enriched stage is necessary, that cohort will be evaluated separately from the initial stage(s) of the trial.

(b) Definition of secondary endpoints:

- i. Safety: Patients will be assessed for toxicities at each clinical evaluation. Toxicities will be graded according to CTC v4.0 standardized grading scales. The incidence of grade 3-5 toxicities will be reported. Patients will be assessed for toxicity as long as they are taking olaparib, for at least 30 days after stopping, and will continue to be followed if olaparib is discontinued for toxicity until the toxicities improve to grade 1 or resolve.
- ii. PSA progression-free survival (PFS): patients in this trial can remain on olaparib as long as they are not experiencing toxicity requiring cessation of drug, not experiencing clinical progression of disease, and until their PSA reaches a value that is double that of the value on enrollment in the study. However, for purposes of reporting this secondary endpoint, a standard definition of PSA progression per PCWG3 will be used. PSA PFS will be defined as an increase in 25% over a nadir value, confirmed by a follow-up PSA at least 4 weeks apart. The date of PSA progression will be the first value recorded (not the confirmatory value). If patients are removed from study prior to PSA progression, then they will be censored at that time.
- iii. Time to PSA doubling from baseline: this endpoint is a time-to-event defined as time from initiation of olaparib therapy until the PSA has increased to 200% of baseline value, confirmed with another measurement at least 4 weeks later. The date of PSA doubling will be the first value recorded (not the confirmatory value).
- iv. Undetectable PSA: A durable undetectable PSA endpoint will be defined as a patient on study with olaparib who achieves a PSA < 0.1, lasting at least 12 weeks. This endpoint will represent a durable complete biochemical response to olaparib. This endpoint can only be achieved while on therapy with olaparib, although the confirmatory values after initially achieving undetectable PSA may be measured while off therapy for olaparib.

(c) Analytic plan for primary objective: We will estimate the PSA₅₀ response rate for the unselected population of patients. If a biomarker-selected population is accrued, it will be analyzed separately from the previously accrued unselected population. If a

biomarker-selected population is not accrued, analysis of response rates for “biomarker-positive” and “biomarker-negative” subjects, based upon the pre-specified gene list, will be reported as exploratory objectives.

(d) Analytic plan for secondary objectives:

- i. Toxicity: these will be reported as a tabulated table by type and grade
- ii. PSA PFS: We will use the Kaplan-Meier method to estimate the median PSA PFS.
- iii. Time to PSA doubling from baseline: We will use the Kaplan-Meier method to estimate the median time to PSA doubling.
- iv. Undetectable PSA: the durable complete PSA response rate will be estimated as number of patients achieving a durable complete PSA response divided by enrolled patients with a 95% confidence interval.

(e) Analytic plan for exploratory objectives:

- i. *(if a biomarker-selected population is not accrued)* Biomarker positive and biomarker negative PSA₅₀ response calculations: All subjects in the trial will be considered either a responder or non-responder based upon the meeting of the primary endpoint based upon the definition above. For each patient, the DNA mutations present in the tumor will be identified through Foundation Medicine sequencing and/or through Personal Genome Diagnostics plasma cell-free DNA analysis. Patients with a deleterious mutation in the pre-specified gene list (ATM, BARD1, BRCA1, BRCA2, BRIP1, CDK12, CHEK1, CHEK2, FANCL, PALB2, PPP2R2A, RAD51B, RAD51C, RAD51D, or other DNA repair genes) will be considered biomarker positive. For biomarker positive and biomarker negative subjects, we will calculate response rates with confidence intervals for hypothesis generation. Separate calculations for each testing modality will occur.
- ii. Development of gene signature for response: based upon the responders and the DNA mutations identified through sequencing, a discovery of a biomarker set will take place with grouping of mutations associating with response.
- iii. RNA expression profile signature positive and negative PSA₅₀ response calculations: Similarly to above, subjects will have tumor tested with RNA expression profiling and scored for likelihood for response to olaparib per the Decipher GRID platform (GenomeDx). For subjects considered to have a positive RNA expression signature based upon a binary score assigned via the GenomeDx proprietary algorithm, a PSA₅₀ response rate will be calculated. Similarly, a calculation will be performed for subjects considered to have a negative RNA expression signature.
- iv. PARP-1 and γ H2AX protein levels: Subjects will have prostatectomy samples analyzed for baseline PARP-1 and γ H2AX proteins, and scored for positivity by immunohistochemistry on scale of 0 (none) to 3 (intense staining), and the results will be associated with responses for both proteins, separately.
- v. Metastasis-free survival analysis: the median MFS will be estimated using the Kaplan-Meier method.
- vi. Time to next anti-cancer therapy analysis: similarly to MFS, this time to event analysis will be estimated using the Kaplan-Meier method.

(f) Sample size justification: The study will enroll up to 50 subjects. The design is a multi-stage adaptive design, with stage sizes and decision rules calculated based upon assumptions for hypothesis testing for the primary endpoint.

The sample sizes for each stage are chosen to allow for interim assessment of the primary endpoint, in order to adapt if the unselected population results are suggestive of futility. In the case of futility in the all-comer population, a biomarker-selected stage can proceed. The operating characteristics of the design were assessed in a 10,000-iteration simulation, assuming biomarker prevalence is 10-15%. This design will have 0.90-0.91 power for the unselected population and a 0.79-0.80 power for the biomarker-selected population when no effect in the selected population. The overall type 1 error is 0.1 – 0.11,. The type 1 error for the biomarker-selected population is 0.04.

The trial will also employ an early stopping rule for an AE of special interest. If >1 patient is diagnosed with myelodysplastic syndrome or acute myeloid leukemia during the trial, then the trial is to be stopped.

Funding, Regulatory, and Feasibility Issues: AstraZeneca is providing funding for performance of the clinical trial as well as providing olaparib to patients. IND will be filed and held by the principle investigator, [name].

Patient Acceptability/Ethics and Consent Issues: This trial will be an alternative option for intervention other than standard therapies of ADT or surveillance. Olaparib has rare but life threatening side effects including MDS/AML in <1% of patients treated; by monthly laboratory monitoring and exclusion of patients with prior chemotherapy, we aim to minimize this risk. Additionally, by performing this trial in the highest risk patients with biochemically recurrent prostate cancer and by exclusion prior DNA-damaging chemotherapy, the potential benefits of a new therapy option with olaparib is more likely to outweigh risks, than if this trial were performed in patients with less risk for morbidity and mortality from prostate cancer.

TABLE OF CONTENTS

[Press F9 to update]

1.1	Disease Background	16
1.2	Treatment Background	17
1.3	Rationale for olaparib in high risk biochemically recurrent prostate cancer	20
2. OBJECTIVES		22
2.1	Primary Objective	22

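### Metastasis-free survival is timed from biochemical recurrence without allowance for metastasis-free entry, so its Kaplan-Meier curve is biased upward and includes time before olaparib (minor, exploratory endpoint)

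*Combined protocol and SAP*

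**What the plan says.** The synopsis, under Exploratory Endpoints, defines "Metastasis-free survival, defined as time from biochemical recurrence to radiographic development of metastatic disease". The next item has the same origin: "Time to next anti-cancer therapy, defined as time from biochemical recurrence to date of administration of prostate cancer therapy (such as ADT", where the quote stops inside a list of example therapies. Section 8 does not cover these endpoints, and section 10 does not restate their origin.

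The estimator is ordinary Kaplan-Meier for both, in the synopsis (Statistical Methods (e) v and vi) and in sections 10.1.2.5 and 10.1.2.6; for next therapy, "similarly to MFS, this time to event analysis will be estimated using the Kaplan-Meier method". No delayed entry or landmark is mentioned.

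Entry requires "No radiographic evidence of metastatic disease by CT scan and bone scan, performed within the prior 4 weeks" (synopsis Inclusion 6; section 3.3), and section 3.4 excludes metastatic disease.

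The secondary endpoints use another clock: "PSA progression-free survival, defined as a time from initiation on olaparib therapy until PSA increase of 25" per cent. Time to PSA doubling also starts at olaparib initiation (synopsis Secondary Endpoints; sections 8.1.2.2 and 8.1.2.3).

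On imaging, "CT scans and NM bone scans will be performed every 6 months for patients remaining on olaparib treatment". Section 5.6 adds scans when a man leaves the study if none were done in the prior 3 months.

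**The concern.** A man who developed metastases between recurrence and screening could not enrol. Ordinary Kaplan-Meier from recurrence nevertheless treats every enrolled man as at risk throughout that interval. This time is event-free by selection, and none of it was spent on olaparib.

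Estimating median metastasis-free survival is a listed objective, and the background sections give natural-history medians with which a reader may informally compare it. A curve that starts with a stretch in which nobody could fail looks better than the disease course it is meant to describe, even if the drug does nothing.

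**Working it through.** **Figure to reproduce.** None. The documents give no target median, event count or power for this endpoint.

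**Direction.** Let T be time from recurrence to metastasis and E time from recurrence to entry. Only men with T > E enrol. For men with the same gap e, the curve from recurrence estimates P(T > t | T > e), which equals P(T > t) / P(T > e) for t ≥ e and 1 for t < e. It is never below P(T > t). When gaps differ, men who have not yet entered inflate the early risk sets, so the estimated hazard is too low. The shift is upward whatever the gap.

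**Size: inputs.**
- PSA at recurrence: 0.2 (section 1.1.2).
- PSA at entry: at least 1 ng/ml; doubling time at most 6 months (section 3.3).
- Median metastasis-free survival: 12 months for doubling time under 3 months, 48 months for 3 to 9 months (section 1.1.3). I assume that these run from recurrence and place a doubling time of 3 months in the second band.
- Gap from recurrence to entry: not given. I assume constant doubling from 0.2 to exactly 1.0. This does not fit men after salvage radiation or ADT, or with persistent PSA.

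**Gap.** log2(1.0/0.2) = 2.32 doublings. Multiplied by doubling times of 1.5, 3 and 6 months, this gives 3.48, 6.97 and 13.93 months.

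**Shifted median.** For a Weibull time with true median m and shape k, setting P(T > t) / P(T > g) to one half gives t = m × (1 + (g/m)^k)^(1/k).

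| Gap g (months) | True median m (months) | k = 1 (exponential) | k = 1.5 |
|---|---|---|---|
| 3.48 | 12 | 15.5 (+29%) | 13.2 (+10%) |
| 6.97 | 48 | 55.0 (+15%) | 49.8 (+4%) |
| 13.93 | 48 | 61.9 (+29%) | 52.9 (+10%) |

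**Is a median reached?** Trials of 50 men on an inert drug were simulated, with doubling times uniform from 1.5 to 6 months and event times treated as exact. True medians were either the two bands above or a single 24 months (synopsis, Disease Background), with shape 1 or 1.5.
- Observation ended at max(3, doubling time) + 2 months after first dose, which approximates treatment to PSA doubling plus confirmation and the end-of-treatment visit. There were about 7 to 8 events. No median was reached in 86% to 98% of runs from recurrence and 98% to 100% from first dose.
- With four times that follow-up, the recurrence-based median was reached in about 47% to 100% of runs.

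**The curve under the shorter follow-up.** At 12 months, the recurrence-based estimate was about 0.90 to 0.91, against a true 0.71 to 0.79. From first dose, the 6-month estimate was 0.83 to 0.86, against a true 0.84 to 0.85, so re-timing removes the distortion.

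**Delayed entry instead?** Keeping the recurrence origin and letting men join the risk set at first dose is the usual alternative. In the two-band model, doubling time sets both the gap and the hazard. There the 12-month estimate was about 0.69 to 0.70, against a true 0.74 to 0.79. It is also noisy: under the shorter follow-up it appeared to reach a median in 21% to 27% of runs, against 2% to 14% for ordinary Kaplan-Meier from recurrence.

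**The case against.** The origin is stated openly, and no comparison, benchmark or decision rule uses this endpoint. Only a median is planned, so the 12-month figures illustrate the bias and are not planned outputs. On the shorter follow-up the median is seldom reached from either origin, so re-timing would rarely change a reported number. All of this stands, and it is why the point is minor. It does not make the recurrence-based curve right.

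Four stronger readings are tempting.

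- *The median will be overstated by a known amount, such as 29%.* The documents give no gap, so the size is an assumption throughout.
- *The median will not be reached, so the origin is immaterial.* That depends on an assumed short follow-up. Section 5.9 plans collection of later therapies and refers to exploratory survival assessments, and section 7.4.3 mentions follow-up for overall survival. Neither schedules imaging, but longer observation is possible.
- *Time to next therapy has the same guaranteed event-free time.* It does not: "prior ADT for biochemical recurrence is allowed, as long as no ADT has been administered in past 6 months" (synopsis Exclusion 1; section 3.4). Nor do the documents support counting that earlier ADT as the event. The word next, the collection of therapies after discontinuation (section 5.9) and the recording of prior ADT as screening history (section 5.1) show the intent. What remains is wording.
- *Men with persistent PSA have no recurrence date.* The synopsis does say "Prior undetectable PSA post-prostatectomy is not required", but section 1.1.2 gives a threshold, confirmed values of at least 0.2 after prostatectomy, that can date most recurrences.

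**Conclusion.** The concern holds for metastasis-free survival. Its origin, ordinary Kaplan-Meier and the metastasis-free entry requirement together bias the curve, and any median reached, upward and include time before olaparib. This direction needs no assumption about the gap.

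The size does. For gaps of 3.5 to 14 months the median rises by about 4% to 29%, given constant PSA doubling, section 1.1.3 medians that run from recurrence, and exponential or shape-1.5 Weibull times. Whether any median is reached turns on follow-up for metastasis after treatment, which is not scheduled.

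A reader might infer that the trial's efficacy conclusion is affected. It is not: the conclusion rests on PSA50 response. For time to next therapy the point is a clarification. Severity: minor.

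**What to change.** In the synopsis (Exploratory Endpoints) and section 10.1.2.5, time metastasis-free survival from the first dose of olaparib, the origin already used for PSA progression-free survival and time to PSA doubling.

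For consistency, use the same origin for time to next anti-cancer therapy (synopsis and section 10.1.2.6), and state that the event is the first prostate cancer therapy started after the first olaparib dose.

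Do not add a supportive delayed-entry estimate from recurrence. It is noisy, and it is biased when PSA doubling time drives both the gap and the risk.

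The cost is the wording of two exploratory definitions. No patients, visits or scans are added, and section 5.9 already collects later therapies. The times will be shorter and will no longer share an origin with recurrence-based natural-history figures. Re-timing alone does not ensure that a median is reached.
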